The primary outcome of this clinical trial is to evaluate the effectiveness of GLUMA in controlling the immediate post treatment sensitivity following occlusal composite restorations. Hence, all the patients were assessed for post restoration sensitivity after 24 hours, 48 hours and at the end of one week. The secondary outcome was to assess whether patient had post-operative sensitivity due to any trigger stimulus. This was also assessed at the end of 24 hours, 48 hours and one week post-operatively.

Post-operative sensitivity and trigger factors (if any) after 24 and 48 hours were assessed with VAS score (1- 10) through telephonic call by a resident student who are unaware of the treatment allocation group. In this study a 1-10 scale were used and the patient is asked to choose a number ranging from 1 to 10 based on their sensitivity, with 1 being the least sensitivity and 10 being the most.

Post-operative sensitivity and trigger factors (if any) after one week were checked by recalling and clinically assessing the patients using Schiff cold air sensitivity scale by a blinded EPGS.

Statistical Analysis

Data was assessed (IBM SPSS Version 23, USA) for normality using the Shapiro-Wilk test. Non-parametric Kruskal-Wallis test and Mann Whitney U test are employed for difference in post treatment sensitivity score among the different groups.

DETAILED DESCRIPTION

Introduction One of the most widely used esthetic restorations in dentistry is composite. Despite the indispensable value that composite brings to a dentist's arsenal, the postoperative sensitivity following composite resin restorations are an undesirable outcome often leading to patient discomfort. ¹This sensitivity

is primarily caused by dentinal fluid movement within exposed tubules, which can be exacerbated by adhesive protocols that do not adequately seal the dentin (Pashley *et al.*, 2002)², micro gaps caused by polymerization shrinkage (Loguercio *et al.*, 2004)³, dentin desiccation and bond degradation over time, potentially due to matrix metalloproteinase (MMP) activation (Mazzoni A *et al.*, 2015)⁴. It's been reported that during the first week after placement of Class I posterior composite restorations, 23% of the patients experienced post-operative sensitivity.⁵

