Post –operative sensitivity after 24 and 48 hours were assessed with VAS score (1- 10) through telephonic call by a resident student who are unaware of the treatment allocation group. The Visual Analogue Scale (VAS) is a common and effective tool for assessing pain and other subjective symptoms, including postoperative sensitivity. In this study a 1-10 scale were used and the patient is asked to choose a number ranging from 1 to 10 based on their sensitivity, with 1 being the least sensitivity and 10 being the most. The advantages of VAS scale is its simplicity, ease of use and applicability.

Post-operative sensitivity after one week all the patients were recalled and clinically assessed by Schiff cold air sensitivity scale by an Experienced Post Graduate Supervisor (EPGS) who is unaware of the allocated treatment groups and those patients with post-operative sensitivity of VAS > 3 were considered for the results (Berkowitz G *et al* 2013)¹¹. A statistician also looked at the treatment results without knowing anything about them.

Schiff cold air sensitivity scale is used to check for post-operative sensitivity which measures a patient's response to a cold air stimulus, helping to gauge the level of sensitivity in a tooth. The procedure involves directing a stream of air at the tooth and observing the patient's reaction, with scores ranging from no response to severe pain (intensity) requiring immediate discontinuation of the stimulus.

The secondary outcome was to assess whether patient had post-operative sensitivity due to any trigger stimulus. This was assessed at the end of 24 hours, 48 hours and one week post-operatively. At 24 hours and 48 hours through telephonic call a resident student who is unaware of the treatment allocation group questioned the patients those who had post-operative sensitivity whether the sensitivity is due to any stimuli (upon mastication/ intake of hot or cold) or spontaneous.

At the end of one week the patients were recalled checked for post-operative sensitivity using both Schiff Air Scale and those patients with post-operative sensitivity of VAS > 3 were questioned whether sensitivity is due to any stimuli¹¹ (upon mastication/ intake of hot or cold) or spontaneous.

STATISTICAL ANALYSIS PLAN

DEFINITION:

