All statistical analyses were performed using non-parametric tests due to the non-normal distribution of the data, as confirmed by both the **Kolmogorov–Smirnov** and **Shapiro–Wilk** tests

($p < 0.001$). Descriptive statistics including mean and standard deviation (Mean \pm SD) were calculated for each of the six desensitizer groups at different time points: Pre-operative, 24 hours, 48 hours, and 1 week post-operative sensitivity, measured using the Visual Analog Scale (VAS).

For intergroup comparisons across all six desensitizer protocols, the **Kruskal–Wallis test** was used independently for each time point. This non-parametric method was selected to assess statistically significant differences in median VAS ranks among the groups, given the violation of normality assumptions. A separate p -value was generated for each time point:

- Pre-operative VAS: $p = 0.003$ (significant)
- 24-hour VAS: $p = 0.126$ (not significant)
- 48-hour VAS: $p = 0.050$ (borderline)
- 1-week VAS: $p = 0.013$ (significant)

Pairwise comparisons between the **Total-etch control** and **Self-etch control** groups were performed using the **Mann–Whitney U test**. This analysis revealed a statistically significant difference in pre-operative VAS scores ($p = 0.012$), while post-operative scores showed no significant differences at 24 hours ($p = 0.337$).

Mean pain scores (VAS) were also summarized for each group at all four-time intervals. The **self-etch Gluma prior to etching group consistently showed the lowest VAS scores** at all time points, suggesting reduced post-operative sensitivity in this group.

Given the minimal differences in outcome scores among the other groups, and the slightly better performance of the self-etch GLUMA prior to etching group, the data suggest that **most treatment protocols were non-inferior** to the best-performing group. Therefore, the trial was interpreted as

a **non-inferiority study**, evaluating whether the other etching and desensitizing protocols were not clinically worse than the most effective group.

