A significance level of $p < 0.05$ was considered statistically significant throughout the analysis. In the present study, the Kruskal-Wallis test was used to compare six desensitizer groups at different time intervals (Pre-operative, 24 hours, 48 hours, and 1 week post-operatively) based on Visual Analog Scale (VAS) scores. Since each time point represents a distinct clinical endpoint, a separate Kruskal-Wallis test was conducted for each, yielding **individual p-values** corresponding to each time point. As the Kruskal-Wallis test does not permit aggregation of multiple outcomes into a single p-value, **a common p-value is not statistically appropriate**.

Ranks

	Desensitizer Group	N	Mean Rank	P Value ^a
Pre Op VAS	Total etch control	86	105.48	0.003
	Total etch Gluma prior to etching	94	141.70	
	Total etch Gluma after etching	86	116.12	
	Self etch control	82	142.30	
	Self etch Gluma prior to etching	80	106.20	
	Self etch Gluma after etching	76	147.55	
	Total	504		
Post Op sensitivity 24hr VAS	Total etch control	86	125.47	0.126
	Total etch Gluma prior to etching	94	122.94	
	Total etch Gluma after etching	86	117.62	
	Self etch control	82	136.49	

	Self etch Gluma prior to etching	80	125.30	
	Self etch Gluma after etching	76	132.62	
	Total	504		
Post Op sensitivity 48hr VAS	Total etch control	86	131.74	0.050
	Total etch Gluma prior to etching	94	127.98	
	Total etch Gluma after etching	86	123.48	
	Self etch control		132.76	
	Self etch Gluma prior to etching	80	114.36	
	Self etch Gluma after etching	76	128.18	
	Total	504		
Post Op sensitivity 1 week VAS	Total etch control	86	124.24	0.013
	Total etch Gluma prior to etching	94	130.96	
	Total etch Gluma after etching	86	124.38	
	Self etch control	82	129.76	
	Self etch Gluma prior to etching	80	115.00	
	Self etch Gluma after etching	76	134.53	
	Total	504		

p < 0.05 denotes statistically significant difference. All the values exhibit non – statistically significant difference. Statistical test applied *

Kruskal – Wallis test

Ranks

	Desensitizer Group	N	Mean Rank	*P Value
Pre Op VAS	Total etch control	86	36.83	0.012
	Self etch control	82	48.45	

	Total	168		
Post Op sensitivity 24hr VAS	Total etch control	86	40.67	0.337
	Self etch control	82	44.41	
	Total	168		

p< 0.05 denotes statistically significant difference. All the values exhibit non – statistically significant difference except the pre operative pain scores. Statistical test applied * Mann Whitney U test

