DESINSENSITIZING AGENT	Pre Op VAS	Post Op VAS (24 hrs)	Post Op VAS (48 hrs)	Post Op VAS (1 week)
	Mean±SD	Mean±SD	Mean±SD	Mean±SD
Total etch control	0.86±1.67	0.37±1.05	0.37±1.05	0.21±0.77
Total etch Gluma prior to etching	1.72±2.15	0.49±1.33	0.40±1.12	0.23±0.81
Total etch Gluma after etching	1.16±2.07	0.28±0.93	0.28±0.93	0.26±0.95
Self etch control	1.88±2.25	0.66±1.32	0.41±1.00	0.12±0.33
Self etch Gluma prior to etching	0.63±1.05	0.20±0.46	0.03±0.16	0.08±0.27
Self etch Gluma after etching	2.11±2.40	0.61±1.31	0.37±0.97	0.21±0.53

- **ESTIMATION PARAMETER:** Mean Difference (Final Values)

ESTIMATED VALUE:

The mean post-operative sensitivity at 1 week was 0.18 units lower in the **Self-etch Gluma prior to etching** group compared to the **Total etch Gluma after etching** group, indicating that the former resulted in reduced sensitivity following restoration.

CONFIDENCE INTERVAL: 95%

NUMBER OF SIDES: 1 – sided

LOWER LIMIT:

Estimation Parameter: Mean Difference (Final Values)

Estimated Value: +0.18

Lower Limit (95% CI, one-sided): +0.003

Parameter Dispersion Type: Standard Deviation

Dispersion Value: 0.1077

The dispersion represents the standard deviation of the difference in mean post-operative sensitivity between the two groups.

Age limits: Patient aged between 15 to 70 years of both the gender were included

Healthy volunteers only/ with disease and why: The reason only healthy individuals are often enrolled because this helps to ensure that any observed effects are specifically related to dentin hypersensitivity and not influenced by other factors, such as an impaired immune response that could be present in individuals with certain systemic conditions.¹²

Investigator's Info:

First name: [name] **Middle name:** Nil **Last name:** [name]

Degree: MDS (Master of Dental Surgery)

[contact]

Email ID: [contact]

College Info: CSI College of Dental Sciences and Research, Madurai (CSICDSR)

(Affiliated under TN [name] University, Chennai, India)

Individual Patient sharing: Individual patient details are often not shared in this research due to concerns about privacy, confidentiality, and potential harm to participants, as well as practical and logistical challenges.¹³

References:

1. Porto I. Postoperative sensitivity on direct resin composite restorations: Clinical practice guidelines. *Indian J. Restor. Dent.* 2012; 1:1–12.

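### The one-week outcome is defined as a blinded Schiff score, but the SAP analyses a one-week 'VAS' and reports no Schiff result; the VAS range and the VAS > 3 rule do not fit the printed tables

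*Combined protocol and SAP*

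**What the plan says.** **One-week measure.** The Brief Summary says one-week sensitivity was checked by recalling and "clinically assessing the patients using Schiff cold air sensitivity scale by a blinded EPGS" (the supervisor). The Outcome measures section of the Detailed Description repeats that "all the patients were recalled and clinically assessed by Schiff cold air sensitivity scale". VAS collection is described only for 24 and 48 hours, by telephone.

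**VAS range.** Outcome measures says "the patient is asked to choose a number ranging from 1 to 10 based on their sensitivity, with 1 being the least sensitivity".

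**VAS > 3.** The same section uses this threshold in two ways. In the one-week primary assessment, "those patients with post-operative sensitivity of VAS > 3 were considered for the results". In the secondary outcome, patients were checked "using both Schiff Air Scale and those patients with post-operative sensitivity of VAS > 3 were questioned" about triggers.

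**What the SAP analyses.** The Procedure section lists the time points and describes the outcome as "and 1 week post-operative sensitivity, measured using the Visual Analog Scale (VAS". The Kruskal-Wallis table has a block labelled "Post Op sensitivity 1 week VAS" with p = 0.013. The Estimated Value entry reads "The mean post-operative sensitivity at 1 week was 0.18 units lower in the" self-etch Gluma-prior arm than in the total-etch Gluma-after arm. Schiff appears nowhere in the SAP, and the SAP states no VAS > 3 rule.

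**The concern.** A Schiff score is an examiner's grading of the response to a cold-air stimulus. A VAS is the patient's own rating. They are different outcomes. The protocol says the first was obtained on everyone at one week, by a blinded assessor, yet no analysis of it is given. The second is analysed, but who took it at one week, and how, is not described. One week matters most because it supplies the only post-operative p-value printed below 0.05 and the only effect estimate.

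Two descriptions of the VAS add to the doubt. A scale that starts at 1 cannot have a mean below 1. And a rule that admits only patients with VAS > 3 to the results would, read literally, select patients on the outcome being compared.

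**Working it through.** **1. Which column gives the estimate.** The mean table gives, at one week, total-etch Gluma after 0.26±0.95 and self-etch Gluma prior 0.08±0.27. Difference: 0.26 − 0.08 = 0.18. With the planned 84 per arm, SE = √(0.95²/84 + 0.27²/84) = √(0.9754/84) = 0.1078. The one-sided 95% lower limit is 0.18 − 1.645 × 0.1078 = 0.0027. The SAP prints 0.1077 and +0.003. So the estimate comes from the one-week VAS column, not from a separate Schiff result.

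**2. VAS range.** All 18 post-operative means are below 1 (0.03 to 0.66), as are 2 of the 6 pre-operative means (0.86 and 0.63). No scores on a 1-10 scale can give these.

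**3. Was VAS > 3 applied to the tables?**
- If only scores above 3 were kept, every mean would exceed 3. None does.
- If scores of 3 or less were set to 0, the SD would be at least √(3m − m²). At m = 0.08 that is 0.48 (printed 0.27); at m = 0.12 it is 0.59 (printed 0.33).

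Neither reading fits, so the rule was not applied.

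**4. How many units were ranked.** The one-week mean ranks weighted by half the printed Ns (43, 47, 43, 41, 40, 38) average 31,878.08/252 = 126.50 = (252 + 1)/2. For 504 units the average would be 252.5. The ranks therefore imply 252 observations.

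**5. Scores behind the one-week means.** Assume whole-number scores from 0 to 10. All score sets that match each printed mean and SD to rounding at those half Ns are:

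| Arm | n | Mean±SD | Possible non-zero scores | Scores > 3 | Mean rank over the 8 combinations | Printed rank |
|---|---|---|---|---|---|---|
| Total-etch control | 43 | 0.21±0.77 | 4,3,1,1 or 3,3,3 | 0-1 | 121.56-125.87 | 124.24 |
| Total-etch Gluma prior | 47 | 0.23±0.81 | 5,2,1,1,1,1 or 4,3,2,2 | 1 | 123.99-129.52 | 130.96 |
| Total-etch Gluma after | 43 | 0.26±0.95 | 6,1,1,1,1,1 or 4,4,3 | 1-2 | 122.50-130.30 | 124.38 |
| Self-etch control | 41 | 0.12±0.33 | five 1s | 0 | 126.44-129.13 | 129.76 |
| Self-etch Gluma prior | 40 | 0.08±0.27 | three 1s | 0 | 120.69-123.50 | 115.00 |
| Self-etch Gluma after | 38 | 0.21±0.53 | 2,2,1,1,1,1 | 0 | 131.53-133.87 | 134.53 |

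Scores above 3 total 2 to 4 of 252. At the printed Ns the same search gives 0-3, 1-3, 1-5, 0 and 0, that is 2 to 11 over five arms. The sixth arm (0.21±0.53 at n = 76) has no whole-number solution.

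**6. Rank table against mean table.** None of the 8 combinations reproduces the printed ranks. Setting self-etch Gluma prior to all zeros does, with 3,3,3 in total-etch control, 5,2,1,1,1,1 in total-etch Gluma prior and 4,4,3 in total-etch Gluma after. The 252 scores then hold 229 zeros, whose mid-rank is (229 + 1)/2 = 115.00, and all six ranks agree within 0.005. Three scores exceed 3. With zeros in that arm, the 0.18 estimate would be 11/43 − 0 = 0.26.

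**7. Could the column hold Schiff scores?** For scores from 0 to k with mean m, the largest SD is √(m(k − m)n/(n − 1)). With m = 0.26, allowing for rounding, this is 0.86 for k = 3 and 1.00 (n = 86) to 1.01 (n = 43) for k = 4. The printed SD of 0.95 therefore needs at least one score of 4 or more. The documents describe Schiff in words only, with no numeric coding, so this does not settle the question.

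**The case against.** The strongest reply is that much of this is loose wording. The secondary-outcome text implies that some VAS was taken at the one-week visit, so the column may be just what its label says. At 24 and 48 hours the trigger question went only to patients who had sensitivity, so some had none; recording them as 0 explains every mean below 1. The VAS > 3 phrase may define a case of sensitivity and not a filter. The SAP states no such rule and its tables did not use one, so harm from selecting on the outcome is hypothetical. The table conflict rests on a reconstruction. If the column is mislabelled Schiff, relabelling would do and no added analysis would be needed.

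Most of this is fair on the side points. The range is probably a wording error, the filter was not applied to these tables, and the table conflict depends on 252 units and whole-number scores. None of it answers the main point. If the column is a VAS, the Schiff result is missing. If it is Schiff, the label is wrong throughout the SAP. Either way the documents need correcting. The p-value of 0.013 is quoted only as printed; the footnote to the same table calls all the values non-significant, and its reliability is a separate question not relied on here.

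**Conclusion.** The concern holds. The stated one-week measure has no reported analysis, and the instrument behind the one-week test and the 0.18 estimate cannot be identified. This follows from the text alone. The documents show an unreported measure, not a deliberate replacement.

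The range conflict is also certain: 18 of 18 post-operative means are impossible on the scale as defined. The two uses of VAS > 3 are unreconciled. Followed literally as a filter, the rule would leave 2 to 4 of 252 scores, or 2 to 11 over five arms at the printed Ns, assuming whole-number scores from 0.

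The conflict between the rank and mean tables is conditional on the same scoring assumption and on the 252 units that the ranks imply. Under those assumptions it falls in an arm that forms the only estimate, which moves from 0.18 to 0.26. The issue should be corrected before the one-week result is interpreted.

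**What to change.** 1. State which instrument the one-week column holds, who recorded it, and how Schiff is coded. Analyse Schiff as an ordinal one-week outcome over all assessed restorations, with the same arm comparisons, and report one-week VAS as supportive. If the column proves to be Schiff, relabel it everywhere and say whether a one-week VAS exists.
2. Correct the VAS range to the one recorded (0-10 with 0 for no sensitivity, if that is the case); if 1-10 is right, correct the data.
3. Delete VAS > 3 as a filter for the sensitivity results. If it was meant only to select who is asked about triggers, say so. Report the proportion above 3 descriptively, with all assessed restorations in the denominator and no between-arm test, because events are too few.
4. Produce the one-week rank and mean tables from one data file and state its N.

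The cost is at most one added analysis of scores that the protocol says were collected, one rerun of the one-week tables, and wording changes. The downside is that the one-week conclusion may change.

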In this single-blinded clinical trial, the numbers of arms were randomly assigned to six groups. The participants of the study were informed about the trial but were unaware of which treatment group they were allocated to. The clinician and researcher were aware of the groups and treatments given. All patients were allocated using Block randomization. It works by dividing participants into individual blocks and then randomly assigning treatments within each block, ensuring roughly equal numbers in each group within that block. In this clinical trial, a block size of 6 (1, 2, 3, 4, 5, 6) was employed for equal enrolment. The prepared blocks were printed in sheets and patients who met the eligibility criteria were systematically assigned in a continuous fashion. After every 6th patient, the enrolment would continue on to the next block from 1.

Arms (n=84 in each)

Arm 1: Total Etch Control group (No desensitizer application)

Arm 2: Total Etch Gluma prior to acid etchant usage

Arm 3: Total Etch Gluma desensitizer application after acid etchant usage

Arm 4: Self Etch Control group (No desensitizer application)

Arm 5: Self Etch Gluma desensitizer application prior to etching

Arm 6: Self Etch Gluma desensitizer application after self-etch adhesive usage

Materials and Methodology

Caries excavation was done using diamond burs (Mani Co., Tochigi, Japan) with water coolant. Cavity extent was until sound hard or firm discolored or non-discolored dentin was achieved. This was cross-checked by an Experienced Post Graduate Supervisor (EPGS) blinded to treatment allocation group. Those teeth with width of the cavity preparation were no more than 1/3rd of the inter-cuspal width were included. Radiographs (Durr PSP Sensor, Durr, Germany) are taken to assess the depth of the

preparation and Remaining Dentin Thickness (RDT). Two RDT measurements from mesial and distal pulp horn to floor of the preparation were calculated. Mean RDT was derived from the two readings. Radiograph assessment was done by EPGS. Teeth were excluded from the study if they had pulp exposure or a prepared cavity that did not meet standardization requirements.

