The Kruskal-Wallis test is a non-parametric statistical test used to determine if there's a significant difference between the medians of three or more independent groups. It's an alternative to the one-way ANOVA when the data doesn't meet the assumptions of normality or equal variances.

STATISTICAL ANALYSIS OVERVIEW:

This present study contains six arms whose descriptions have been provided in the brief summary. The statistical analysis was performed using IBM SPSS version 23. The normality was assessed using Shapiro – wilks test and Q -Q plots. Since the groups do not follow the normal distribution Kruskal – Wallis test to test the statistical significance of post operative sensitivity among the groups. Mann – whitney U test was used to assess the post operative sensitivity among the control groups.

GROUPS INVOLVED:

CONTROL GROUPS:

GROUP 1: Total Etch (TE) Control Group

GROUP 2: Self Etch (SE) Control Group

TEST GROUPS:

GROUP 2: TE - GLUMA Application After Acid Etching

GROUP 3: TE - GLUMA Application Prior to Acid Etching

GROUP 5: SE - GLUMA Application Prior to Acid Etching

GROUP 6: SE - GLUMA Application After Acid Etching

NULL HYPOTHESIS:

The null hypothesis states that there is no statistically significant difference in post operative sensitivity on GLUMA application etching before or after total etching or self-etching followed by composite restoration of the carious teeth.

SAMPLE SIZE CALCULATION:

For this clinical trial, a sample size of 504 restorations was calculated to be sufficient for detecting statistical difference using G* power software (α probability error – 0.05 and effect size – 0.2).

TYPE OF ANALYSIS:

The type of trial is a Noninferiority trials. By definition a non – inferiority trial tests whether a new experimental treatment is not unacceptably less efficacious than an active control treatment already in use. With continuous improvements in health technologies, standard care, and clinical outcomes, the incremental benefits of newly developed treatments may be only marginal over existing treatments. (Hahn S. Understanding noninferiority trials. Korean journal of pediatrics. 2012 Nov 23;55(11):403.)

This test is a non - inferiority trial hence the six groups have GLUMA application before etching of a composite restoration which is not unacceptably less efficacious in reducing post operative sensitivity in composite restoration of a carious tooth.

PROCEDURE:

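### The printed mean ranks describe 252 records, not 504, and the 1-week p = 0.013 cannot be obtained from them unless each record is counted twice

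*Combined protocol and SAP*

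**What the plan says.** The SAP's Procedure section runs one Kruskal-Wallis test per time point across six groups and reports p = 0.003 (pre-operative), 0.126 (24 hours), 0.050 (48 hours) and, for the last, "1-week VAS: $p = 0.013$ (significant". The ranks table that follows prints group Ns of 86, 94, 86, 82, 80 and 76, total 504. Its footnote repeats the 0.05 threshold and then states "All the values exhibit non – statistically significant difference. Statistical test applied".

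A second ranks table compares the two control arms by Mann-Whitney test, with N = 86 + 82 = 168. It prints p = 0.012 pre-operatively and 0.337 at 24 hours; for the latter the Procedure text says "post-operative scores showed no significant differences at 24 hours".

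The mean and SD table gives scores close to zero after treatment, for example 0.08±0.27 at 1 week for self-etch Gluma prior to etching. The estimation section then prints "Lower Limit (95% CI, one-sided): +0.003" and "Dispersion Value: 0.1077". The planned size is "Arms (n=84 in each".

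**The concern.** The printed Ns and the printed mean ranks cannot come from the same analysis, because the ranks are about half the size that 504 records would produce. If the p-values were computed on a file holding each record twice, the test statistic is roughly doubled and the p-values are too small.

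One week is one of the three stated times for the primary outcome, and its p-value is the only post-operative result labelled significant. Also at stake is how many independent observations the trial has, which affects every test, the interval and the power. Separately, the text and the table footnote give opposite verdicts on the same p-value.

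**Working it through.** **Inputs.** Mean ranks, Ns and p-values from the two ranks tables; means and SDs from the descriptive table. The blank 48-hour N for self-etch control must be 82 for the total to be 504.

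**1. How many records were ranked.** The N-weighted average of mean ranks must equal (N+1)/2: 252.5 for 504 and 126.5 for 252. Halving the printed Ns gives 43, 47, 43, 41, 40, 38 = 252. The weighted rank sums are then 31,877.9 (pre-operative), 31,878.7 (24 h), 31,877.9 (48 h) and 31,878.1 (1 week), against 252 × 126.5 = 31,878. Each block averages 126.50. The Mann-Whitney blocks average (43 × 36.83 + 41 × 48.45)/84 = 42.50 and (43 × 40.67 + 41 × 44.41)/84 = 42.50, which is (84+1)/2; 168 records would need 84.5.

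**2. Can 252 records give the printed post-operative p-values?** H = 12/[N(N+1)] × Σ nᵢ(R̄ᵢ − 126.5)², divided by the tie factor C = 1 − Σ(t³ − t)/(N³ − N), on 5 df. At 1 week Σ = 9,523.8, so H = 12 × 9,523.8/(252 × 253) = 1.793. Zeros are the lowest tied block, so (Z+1)/2 cannot exceed the smallest mean rank, 115.00, and Z ≤ 229. The strongest correction is 229 zeros with the other 23 scores tied: C = 0.249, H/C = 7.20, p = 0.206. Allowing for rounding of the ranks, the floor is 0.205.

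At 24 and 48 hours the number of zeros is capped by listing all whole-number score sets (0 to 10) that match the printed means and SDs.

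| Time | H | Most zeros | C | Lowest p, 252 records | Printed p |
|---|---|---|---|---|---|
| 24 h | 1.808 | 214 | 0.384 | 0.45 | 0.126 |
| 48 h | 1.748 | 224 | 0.296 | 0.32 | 0.050 |
| 1 week | 1.793 | 229 | 0.249 | 0.206 | 0.013 |

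From the ranks alone, without the mean table, the floors are 0.106, 0.259 and 0.206.

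**3. What reproduces the printed values.** At 24 and 48 hours exactly one score set matches all the means, SDs and ranks (210 and 222 zeros). At 1 week none of the 8 sets matching the means and SDs fits the ranks; one set fits once self-etch Gluma prior is made all zeros (229 zeros, and 115.00 = (229+1)/2). Its non-zero scores are: total-etch control 3, 3, 3; total-etch prior 1, 1, 1, 1, 2, 5; total-etch after 3, 4, 4; self-etch control five 1s; self-etch after 1, 1, 1, 1, 2, 2.

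| Time | p counted once | p counted twice | Printed |
|---|---|---|---|
| 24 h | 0.507 | 0.1256 | 0.126 |
| 48 h | 0.355 | 0.0499 | 0.050 |
| 1 week | 0.207 | 0.0133 | 0.013 |

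**4. Conflict at 1 week.** With n = 40, 0.08±0.27 means three scores of 1. All 8 sets that keep it give p = 0.75 to 0.88 once and 0.38 to 0.61 doubled. The arm's mean rank would be 120.7 to 123.5, not 115.00.

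**5. Pre-operative values.** Doubling turns a mean rank R into 2R − 0.5. The uncorrected doubled tests give H = 29.4 (p = 0.00002) and z = 3.09 (p = 0.002). Tie correction only lowers these, so the printed 0.003 and 0.012 cannot come from doubled records. On 252 and 84 records the uncorrected values are 0.0118 and 0.029, and tie factors of about 0.82 and 0.75 bring them to 0.003 and 0.012. The tables therefore mix sample sizes.

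**6. The 24-hour Mann-Whitney p.** The matched 24-hour controls reproduce ranks 40.67 and 44.41 but give p = 0.316 once and 0.155 doubled, not 0.337. The rank-implied 1-week controls give 0.499 once and 0.337 doubled.

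**7. Side points, both conditional.** The interval: √[(0.95² + 0.27²)/84] = 0.1078 and 0.18 − 1.645 × 0.1078 = +0.003, close to the printed figures at 84 per arm. At 43 and 40 the SE is 0.1510 and the limit −0.07. With the rank-implied scores (difference 11/43 = 0.256, SE 0.1454) it is about +0.02. Power for effect size 0.2 is 0.95 at 504 and 0.67 at 252 if planning used a six-group one-way ANOVA, which the document does not say.

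**The case against.** The strongest reply is that double counting is a reconstruction. Duplicated rows, a case weight of 2 and a different data file cannot be told apart from the document. At 1 week, the value that matters most, the match needs a printed mean to be overridden. That stands, so doubling should be put as the likely explanation. The average of 126.50 and the 1-week floor do not depend on it.

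The 24-hour evidence is weaker. The ranks-only floor of 0.106 does not exclude 0.126, so the misfit there relies on the mean table, which is itself in conflict with the ranks for one arm at 1 week. That also stands.

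The scale is described as running from 1 to 10, while the check uses zeros. Means below 1 force values below 1, so this does not undo the check, but it is an assumption.

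The row mix-up behind 0.337 rests on one numerical match. On ranks alone, 0.337 could fit 84 single records with a tie factor of 0.54; only the means and SDs rule that out. Every candidate value is non-significant, so no conclusion turns on it.

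Finally, the non-inferiority reading and the mean-difference interval do not rest on p = 0.013. That limits the reach of the error but leaves the p-value and the analysed N unsupported.

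**Conclusion.** The concern holds. That the ranks come from 252 and 84 records, not the printed 504 and 168, follows from an identity and needs no assumption about scores. Given those ranks, with zeros as the lowest and largest tie group, the 1-week p is at least about 0.206 on 252 records.

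If 252 independent records are confirmed, 24 hours moves from 0.126 to about 0.51, 48 hours from 0.050 to about 0.355, and 1 week from 0.013 to about 0.21 on the rank-implied scores, or 0.75 to 0.88 if 0.08±0.27 is right. These figures assume whole-number scores from 0 to 10. No post-operative Kruskal-Wallis test would then reach 0.05. The sign of the interval's lower limit is not settled either way.

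The contradiction between the Procedure text and the footnote needs no calculation: 0.003 and 0.013 are both below the 0.05 limit that the footnote itself states. This must be corrected before the results are relied on.

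**What to change.** 1. Check the source data for the number of independent records per arm and for duplicated or weighted rows.
2. Reconcile the 1-week self-etch Gluma-prior scores (all zero by the ranks, 0.08 in the mean table), and establish which time point p = 0.337 belongs to.
3. Rerun every Kruskal-Wallis and Mann-Whitney test and the interval with one record per independent unit and each arm's own n. If 504 distinct scores exist, use them all and account for any patient contributing more than one: the sample size is given as "a sample size of 504 restorations was calculated to be sufficient for detecting statistical difference using G* power software", but allocation is by patient ("After every 6th patient, the enrolment would continue on to the next block from 1").
4. Print N, mean ranks and p-values from the same run, and confirm that the ranks average (N+1)/2.
5. Withdraw the 1-week significance label unless the rerun supports it, and make the Procedure text and the table footnote agree.
6. If 252 is confirmed, restate the analysed N and the power it gives.

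The cost is a source-data check, a rerun of existing analyses and corrected tables. No new patients are needed. The reported results will probably look less favourable.
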